## 1 SYNOPSIS

Title: Neuropsychological Dysfunction and Neuroimaging Abnormalities in Neurologically Intact Adult Patients With Sickle Cell Disease (SCD)

CSCC Protocol Chair: [name].

Intervention: In Phase I, approximately 156 subjects will participate in a cross-sectional study consisting of screening questionnaires, a neuropsychological testing battery, and MRI testing. In Phase II, a subset of approximately 30 participants will be asked to participate in a transfusion intervention. Half will be randomized to undergo a chronic transfusion regimen for six months, and the other half will be treated with standard care alone, guided by their disease symptoms.

Objectives:
 
Primary objective(s): To determine the extent of neurocognitive dysfunction in neurologically asymptomatic adult patients with sickle cell disease.
 
Secondary objective(s): To determine the association between neurocognitive dysfunction and imaging abnormalities.

Hypotheses/Estimates:
 
Primary hypothesis: Neurocognitive testing in neurologically asymptomatic adult sickle cell patients will be abnormal compared to community controls.
 
Secondary hypotheses:
 
 
1. Neurologically intact adults with SCD will have significantly lower scores on other neuropsychological (NP) tests of executive function than adult controls.
 
2. A larger percentage of adult patients with abnormal MRIs will have abnormal NP testing than those with normal MRIs.
 
3. Volumetric MRI will detect brain dysfunction in patients with abnormal neurocognitive tests but normal qualitative MRI.
 
4. Correction of anemia with transfusion therapy will improve the cognitive function in SCD patients with abnormal neurocognitive testing more than standard care.
 
 
Hypothesis testing will apply to the primary hypothesis only; all secondary hypotheses will address issues of estimation.

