## 7 STUDY DESIGN

### 7.1 DESCRIPTION OF PRIMARY AND SECONDARY ENDPOINTS

The primary endpoint is completion of baseline WAIS III-PIQ studies in 120 subjects and 36 controls. Assuming a 20% attrition rate, 150 subjects and 45 controls will be recruited.

Secondary endpoints include completion of the entire baseline NP battery and MRI studies in 120 subjects and 36 controls. After consent and randomization, the final secondary endpoint is completion of the transfusion protocol and demonstration of at least an average five-point within-subject improvement in WAIS-PIQ above any average within-subject improvement observed in the standard care group, total number of patients is 30 (15 in each group). Thirty-six patients meeting these criteria will be randomized, assuming 80% completion. Randomization in the transfusion phase of the study is appropriate in order to discriminate, as much as possible, intervention effects from re-test effects.

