## 9.4 TREATMENTS

Approximately 36 patients with WAIS-III PIQ scores  $\leq 90$  will be asked to participate in a transfusion intervention. Half of these patients will be randomized to undergo a chronic

transfusion regimen for six months, and the other half will be treated with standard care alone, guided by their disease symptoms. At the end of the six-month period, both groups of patients will be re-tested on the neurocognitive battery and the MRI will be re-administered. The mean change scores will be compared between the two groups.

The intervention will involve visits to the center for transfusions. Although it may be argued that benefits to patients receiving the intervention would include those due to the transfusion as well as those that might be due to increased interaction with center staff, it is not feasible to separate the effects of the two in the pilot study. To do so would require a more elaborate study design.

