### 10.5 VISIT SCHEDULE FOR THE PILOT TRANSFUSION TRIAL

Approximately 36 patients with WAIS III-PIQ scores  $\leq 90$  will be asked to participate in Phase II of the study. Half of these patients will be randomized to undergo a chronic transfusion regimen for six months, and the other half will be treated with standard care alone, guided by their disease symptoms.

During the first visit for Phase II, subjects who completed Phase I and went on to Phase II will sign informed consent, be screened for eligibility (including a blood draw for the hematology and chemistry panels), and will have their quality-of-life assessed by the self-administered SF-36. As described above, this can occur at the Visit 4 Debriefing or at a subsequent visit. The SF-36 assesses eight health concepts: 1) limitations in physical

activities because of health problems; 2) limitations in social activities because of physical or emotional problems; 3) limitation in usual role activities because of physical health problems; 4) bodily pain; 5) general mental health (psychological distress and well-being); 6) limitations in usual role activities because of emotional problems; 7) vitality (energy and fatigue); and 8) general health perceptions.

If > 6 months (but < 1 year) have passed since the subject's participation in Phase I of the study, the subject must FIRST repeat the WAIS-III PIQ portion of the Neuropsych Battery at the first visit of Phase II to confirm that the subject's PIQ score is  $\leq 90$ . If the score is still consistent with eligibility requirements, the study coordinator will complete the screening blood draw on the subject, administer the SF-36, and will schedule a repeat MRI so that the image can be compared to the MRI conducted during Phase I. The site will locally confirm that the repeat MRI does not contain any new neurological findings when compared to the Phase I MRI.

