**TABLE 13.2 Sample Size Calculations for a 2-Sided t-test with an SD of 20 and  $n_2 = 0.3n_1$**

Difference in mean WAIS-III Performance IQ between adults with SCD and the control group.	Sample sizes required in each group (2-sided) Cases, Controls*	Power
8	213, 64	0.80
8	244, 74	0.85
8	285, 86	0.90
8	352, 106	0.95
10	137, 42	0.80
10	156, 47	0.85
10	183, 55	0.90
10	226, 68	0.95
15	61, 19	0.80
15	70, 21	0.85
15	81, 25	0.90
15	101, 31	0.95

\* *Sample Size Estimates Assuming 3 Controls for Every 10 Cases. (These do not take data loss into account).*

Observations:

1. If the standard deviation of the WAIS-III is no greater than 15 and the true difference in WAIS III group means is at least eight, then using 120 SCD patients and 36 controls results in at least 80% power for the primary hypothesis.
2. If the standard deviation of the WAIS-III is no greater than 20 and the true difference in WAIS III group means is at least 15, then using 101 SCD patients and 31 controls results in at least 95% power for the primary hypothesis (see Table 13.2).

In order to have sufficient power for the primary hypothesis and sufficient patients recruited for the 4th secondary hypothesis (transfusion study) we would need to enroll 150 patients and 45 controls. Assuming an 80% completion rate, 120 patients and 36 controls would complete the baseline evaluation. (Please refer to observations 1 and 2 above for power estimates.) Assuming a normal distribution, 60 of the 120 patients will have WAIS-III PIQ scores at or below the predicted mean of 85. These patients would be approached to participate in the transfusion study. Assuming 60% would agree to participate and again assuming a completion rate of 80%, 36 patients would be randomized to either the chronic transfusion arm or the standard care arm and 30 would complete the protocol (allowing for 15 in each group).

For power calculations and statistical analysis the 4th secondary hypothesis, the transfusion arm will have a mean WAIS-III PIQ change score that is different than the mean change score in the control arm, can be expressed:

$$H_0: \mu_{\text{diff, trt}} - \mu_{\text{diff, control}} = 0$$

$$H_a: \mu_{\text{diff, trt}} - \mu_{\text{diff, control}} \neq 0.$$

We will use a 2-sample comparison t-test framework for power calculations. To estimate the power of the t-test given 15 subjects per arm, we used the following normal approximation:

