Cortical gray matter and hippocampal volume will demonstrate a more significant correlation with executive and memory cognitive functions than the correlation of WML or lacunar infarcts with these same cognitive functions.

The statistical analysis will not involve a formal hypothesis test, but in statistical terms the hypothesis can be written as:

$$H_0: \rho_{\text{MRI-Nptest-Vol}} - \rho_{\text{MRI-Nptest-Reg}} = 0$$

$$H_a: \rho_{\text{MRI-Nptest-Vol}} - \rho_{\text{MRI-Nptest-Reg}} \neq 0.$$

For this analysis, we will descriptively compare Spearman or Pearson correlations.

The last secondary hypothesis involves randomizing 36 people who had a baseline WAIS-III PIQ score  $\leq 90$  to two treatment groups. We will treat one group with transfusion for 6 months and the other group with standard care for six months. After the six months of treatment we will perform a before and after comparison of the WAIS-III PIQ results, using within subject WAIS-III PIQ change scores as the outcome. We expect that on average patients who receive transfusion will show at least a five-point improvement when retested after six months of transfusion. Although this secondary hypothesis expresses the expected direction of effect independently of the observed affect in the control group, the statistical analysis will follow common practice and first use a 2-sided hypothesis test with an alpha of 0.05 to compare the mean within subject WAIS-III PIQ change score in the two groups. Second, we will calculate a 95% CI for the true effect of transfusion on WAIS-III PIQ within subject change scores for the group who received transfusion. We will use either a t-test, a Wilcoxon Two-Sample test, or a regression model to test the hypothesis. For statistical analysis we can express this secondary hypothesis as the mean within subject change score in WAIS III PIQ for the transfusion group will be different than the mean within subject change score in the control group:

$$H_0: \mu_{\text{diff, trt}} - \mu_{\text{diff, control}} = 0.$$

$$H_a: \mu_{\text{diff, trt}} - \mu_{\text{diff, control}} \neq 0.$$

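### The Phase II PIQ comparison is left open among three tests on raw change scores; one baseline-adjusted model named in advance would hold the error near 5% and remove the effect of chance baseline imbalance

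*Protocol*

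**What the plan says.** Section 13.2 analyses the last secondary hypothesis "using within subject WAIS-III PIQ change scores as the outcome". It will "first use a 2-sided hypothesis test with an alpha of 0.05 to compare the mean within subject WAIS-III PIQ change score" in the two groups, and then: "We will use either a t-test, a Wilcoxon Two-Sample test, or a regression model to test the hypothesis". The null and alternative hypotheses that follow concern the difference in mean change. No rule for choosing is given, and the regression option names no covariate. The only interval that section 13.2 names for this hypothesis is worded for the transfused group, not for the difference between arms.

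Section 9.4 restates the comparison as unadjusted: "The mean change scores will be compared between the two groups". The power calculation in section 13.1 is also built on change scores: "To estimate the power of the t-test given 15 subjects per arm".

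The Synopsis gives the hypothesis another status: "Hypothesis testing will apply to the primary hypothesis only; all secondary hypotheses will address issues of estimation".

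**The concern.** Three procedures share one 0.05 test. If the choice were made after seeing the data, the stated error rate would no longer hold.

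The second issue is the raw change score. Eligibility requires a PIQ of 90 or less, so every randomised patient has a baseline value. With about 15 completers per arm, the arms can differ at baseline by chance. When the correlation between the two tests is below 1, the arm that starts lower tends to gain more, with or without treatment. Part of the imbalance therefore appears in the difference in change. A model with baseline PIQ as covariate uses data already collected to remove it.

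**Working it through.** **Inputs.** From section 13.1: 15 per arm, SD 15 at both times, correlation ρ of 0.70 (five-point difference) or 0.80 (ten-point difference), two-sided 0.05, predicted patient mean 85. From sections 9.2 and 13.2: baseline PIQ of 90 or less. Assumption for the selected case: PIQ is normal with mean 85 and SD 15 before selection, and ρ describes those unselected patients.

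**1. The protocol's own power figures.** Variance of change = 2 × 225 × (1 − ρ).
- ρ = 0.70: variance 135; SE = √(135 × 2/15) = 4.24; power for five points 21.8% (stated: 22%).
- ρ = 0.80: variance 90; SE = √(90 × 2/15) = 3.46; power for ten points 82.3% (stated: 82%).

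Both reproduce.

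**2. Error from an open choice.** These are simulated trials with no treatment effect: 15 per arm, 20,000 per setting, ρ of 0.70 and 0.80, with and without selection at 90. The regression option is taken as baseline-adjusted.

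| Reported result | Rejection rate |
|---|---|
| Any one test fixed in advance | 4.5% to 5.5% |
| Better of t-test and Wilcoxon | 5.7% to 6.2% |
| Best of all three | 6.9% to 7.4% |

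**3. Baseline imbalance.** The cut at 90 lies (90 − 85)/15 = 0.333 SD above the mean. With λ = 0.3774/0.6306 = 0.5985, the selected baseline variance is 225 × (1 − 0.333 × 0.5985 − 0.5985²) = 99.5, so the SD is 9.98. The SE of the baseline difference between arms is 9.98 × √(2/15) = 3.64 points. The unadjusted change difference shifts by (1 − ρ) × imbalance = 0.30 × 3.64 = 1.09 points at ρ = 0.70, and 0.20 × 3.64 = 0.73 at ρ = 0.80.

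**4. Variance.** The residual variance after adjustment is 225 × (1 − ρ²), which selection on baseline does not alter. The selected change-score variance is that residual plus (1 − ρ)² × 99.5.

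| ρ | Adjusted | Change, unselected | Ratio | Change, selected | Ratio |
|---|---|---|---|---|---|
| 0.70 | 114.75 | 135 | 0.85 | 123.7 | 0.93 |
| 0.80 | 81 | 90 | 0.90 | 85.0 | 0.95 |

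These ratios treat the slope as known. Estimating it multiplies the adjusted variance by about 1 + 1/26 = 1.038, so the net ratios are about 0.88 and 0.93 unselected, and 0.96 and 0.99 selected.

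**5. Power for five points at ρ = 0.70.**

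| Scale | Patients | Change score | Adjusted |
|---|---|---|---|
| Normal approximation | Unselected | 21.8% | 24.8% |
| Normal approximation | Selected | 23.4% | 24.8% |
| t-based (28 df; 27 df with slope cost) | Unselected | 20.7% | 22.7% |
| t-based (28 df; 27 df with slope cost) | Selected | 22.1% | 22.7% |

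**The case against.** Phase II is a pilot and this is the fourth secondary hypothesis, which the Synopsis assigns to estimation. At 22% power for five points, a move from 5% to 7% changes little. Over repeated randomisations the change-score difference is unbiased, and 1.09 points is only about a quarter of its SE (1.09/4.06 = 0.27). The regression option already permits baseline adjustment. A separate statistical analysis plan, not among the documents reviewed, may settle the model.

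Much of this stands, and it rules out several stronger readings:

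- A reader might infer that ANCOVA is what controls the error. It is not: a change-score t-test fixed in advance does so equally well.
- A reader might infer that the trial will run at 7%. The protocol does not say the choice follows the data; 7% is the worst case of reporting the smallest p-value.
- A reader might infer three different estimands. The stated hypothesis is a difference in mean change. The t-test and a regression, with or without baseline, target that difference; only the Wilcoxon test departs from it.
- A reader might infer that adjustment cures the low power. On one consistent scale the gain is 0.6 to 3.0 percentage points.
- A reader might take this as the only randomised comparison. Section 9.4 retests the battery and MRI in both arms, and section 11.8 compares adverse events between arms.

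The objection does not remove the point. Detail left for an analysis plan is not a defect, but here the protocol itself states three alternatives for one 0.05 test.

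**Conclusion.** The concern holds as a limited point about specification and efficiency. An open choice could raise the two-sided error to about 6-7% at worst. At ρ = 0.70, a one-SE baseline imbalance moves the unadjusted estimate by about 1.1 points, about a fifth of the five-point target. Adjustment cuts residual variance by 10-15% on the stated inputs, or about 5-7% under the selection assumption, and by less once slope estimation is counted. The stronger reason for adjusting is protection against chance imbalance; the gain in power is minor. The selected figures rest on normality with mean 85 and SD 15 before the cut, and all figures rest on correlations of 0.70 to 0.80.

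Separately, the Synopsis and section 13.2 contradict each other on whether this hypothesis is tested. An adjusted difference with its interval serves either answer.

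**What to change.** In section 13.2, replace the three options with one analysis: linear regression of six-month PIQ (or change) on randomised arm, with the last PIQ before randomisation as covariate, reporting the adjusted between-arm difference and its 95% CI. Specifying the last value matters because section 10.5 has some Phase I patients repeat the PIQ before randomisation, which leaves two candidate baselines. Keep the Wilcoxon test on change as a sensitivity analysis only.

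Align section 9.4 with this. The section 13.1 power figures can stay if they are labelled as referring to the unadjusted change score. State once, in the Synopsis and in 13.2 alike, whether this hypothesis is tested at 0.05 or only estimated.

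The cost is a few sentences in three or four places, with no new patients or data. The analysis gives up one degree of freedom (27 instead of 28) and estimates one slope.

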## 14 HUMAN SUBJECTS PROTECTION

### 14.1 PURPOSE OF THE STUDY

The purpose of this research study is to determine the extent of memory and attention problems in adults with SCD. Adults who have not experienced a stroke or other brain damage will be asked to join the study. The study will also evaluate the link between these events or conditions and abnormal MRI. These findings will be compared to the results of healthy people with similar backgrounds.

For some participants, testing will show evidence of problems with memory and attention, potentially caused by the anemia that occurs among most patients with sickle cell disease. Correcting anemia has been linked in some non-sickle cell patients with better memory and attention.

A second part of the study will involve treating anemia for a six-month period in a subset of subjects who have completed the neuropsychological testing and MRI, in order to assess the effect of transfusion on memory and attention. This second study phase is a randomized clinical trial in which patients in the treatment arm of the study will receive transfusions over a period of six months as a potential treatment to improve memory. Patients in the non-intervention group will receive no transfusion therapy and will receive their standard treatment.

### 14.2 STUDY PROCEDURES

Hb SS patients and healthy adults are being asked to take part in this study. Patients will have NP testing, behavioral studies, and an MRI test. The schedule of events associated with the study is summarized below:

#### *Visit 1:*

Clinical site staff will review the informed consent process with the potential subject, will answer all questions, and will ensure that the consent is signed and dated by the subject. Following informed consent, clinical staff will conduct a brief screening (the PSS) and the potential study subject will be required to complete two short questionnaires (the POMS and MMSE). Medical records for potential participants with SCD will be reviewed. A history, physical exam, and neurological exam will be completed. For females of childbearing potential, a urine sample will be collected to ensure that the subject is not pregnant. Two teaspoons of blood will be drawn from all potential subjects; for adults with SCD, the blood will be used to confirm the diagnosis, and for the control group, the blood will be drawn to ensure the potential participant is not anemic. The blood drawn will also be used for a hematology and chemistry panel. If the blood draw confirms that the subject (case or control) is eligible for the study, then Visit 2 will be scheduled to conduct the NP testing.

#### *Visit 2 – Neuropsychological Testing or MRI:*

The sequencing of the NP test battery and the MRI is flexible. Therefore, at Visit 2, either the NP test battery or the MRI can be performed. A trained and supervised professional will conduct the NP testing, which will require 6 to 6½ hours to complete. The individual administering the test will score and submit copies of the tests and the results to a study co-PI for validation. MRI testing will be done at the local hospital. The radiologist or imaging tech will document that completion of the MRI has occurred. Following testing, an appointment for Visit 3 will be scheduled.

***Visit 3:***

At Visit 3, the component of the study that was not completed at Visit 2 will be completed, i.e., either the NP Battery or the MRI.

***Visit 4:***

Upon completion of Phase I of the study, all subjects, including those with SCD and those recruited as controls, will be debriefed about the results of their evaluation. This debriefing should include a face-to-face discussion about the results of the evaluations.

**Phase II visits:**

A approximately 36 patients with sickle cell disease will be asked to participate in an intervention study (Phase II) in which subjects will be randomized to either a transfusion arm or a standard care arm. After informed consent and eligibility screening is complete, the SF-36 will be administered to all patients, followed by randomization to either the treatment or control groups. For females of childbearing potential, a urine sample will be collected to ensure that the patient is not pregnant.

If more than 6 months but less than 1 year has passed since the subject's participation in Phase I of the study, the subject must FIRST repeat the WAIS-III PIQ portion of the Neuropsych Battery at this visit to confirm that the subject still has a score of  $\leq 90$ . If the score is still consistent with eligibility requirements, the study coordinator will complete the screening blood draw on the subject, administer the SF-36, and will schedule a repeat MRI so that the image can be compared to the MRI conducted during Phase I. The site will locally confirm that the repeat MRI does not contain any new neurological findings when compared to the Phase I MRI.

If > 1 year has passed since the subject's participation in Phase I (or if the subject was not enrolled in Phase I), the subject must complete the MMSE and the POMS, as well as the WAIS-III PIQ portion of the Neuropsych Battery to confirm eligibility. If eligible, the study coordinator will complete the screening blood draw and schedule an MRI to be completed at Visit 2. (For subjects enrolled in Phase I, this is a repeat MRI that should be compared to the Phase I MRI to confirm there are no new neurological findings. If eligible to continue, the subject will return for Visit 3, during which the SF-36 and the remainder of the Neuropsych Battery is administered and the subject is randomized.

At Visit 2, the subject will complete the MRI. The MRI will be read locally to confirm eligibility requirements. If the subject does not meet the criteria, he/she will be discontinued from the study without completing any additional assessments.

At Visit 3, the subject completes the remaining NP Battery tests (other than the PIQ), the SF-36, and is then randomized.

Individuals randomized to the treatment arm will receive simple transfusions and additional blood testing every 3 to 4 weeks. A blood sample will be sent to the study laboratory before each transfusion. Individuals randomized to the treatment arm will receive the same general care for SCD as those who are not randomized to treatment.

Individuals randomized to the standard care arm will have monthly contact with clinic staff to complete an interval history form, and to have blood drawn (at Months 3 and 6) for a Hematology and Chemistry panel and to measure ferritin levels. All patients will be taught the signs and symptoms of stroke and asked to report any such signs.

After 6 months of treatment, both groups will complete another NP Battery and SF-36. A new MRI must be completed within 2 weeks after the NP Battery.

